2.5. Secondary Efficacy Variables

Secondary efficacy variables are as follows:

- Incidence of very severe RSV LRTI defined as RSV LRTI hospitalization with oxygen saturation < 90% (at any time during hospitalization) and oxygen supplementation, through the RSV season
- Incidence of RSV LRTI hospitalization through the RSV season in each country
- Incidence of hospitalizations for all-cause LRTI through the RSV season
- Incidence of RSV LRTI hospitalization through Day 151 post-dosing/randomization (overall and in each country)
- Incidence of very severe RSV LRTI defined as RSV LRTI hospitalization with oxygen saturation < 90% (at any time during hospitalization) and oxygen supplementation, through Day 151 post-dosing/randomization (overall and in each country)
- Incidence of hospitalizations for all-cause LRTI through Day 151 post-dosing/randomization (overall and in each country)
- Incidence of RSV LRTI hospitalization through Day 181 post-dosing/randomization (overall and in each country)
- Incidence of hospitalizations for all-cause LRTI through Day 181 post-dosing/randomization (overall and in each country)
- Incidence of RSV LRTI hospitalization from 181 days post-dosing/randomization until Day 366 (overall and in each country)

- Incidence of hospitalizations for all-cause LRTI from 181 days post-dosing/randomization until Day 366 (overall and in each country)
- Incidence of RSV LRTI hospitalization in UK reconsented participants from Day 366 post-dosing/randomization to Day 731 post-dosing/randomization
- Incidence of hospitalizations for all-cause LRTI in UK reconsented participants from Day 366 post-dosing/randomization to Day 731 post-dosing/randomization
- Incidence of recurrent wheeze events in UK reconsented participants through Day 366 post-dosing/randomization
- Incidence of recurrent wheeze events in UK reconsented participants from Day 366 to Day 731 post-dosing/randomization
- Incidence of recurrent wheeze events in UK reconsented participants through Day 731 post-dosing/randomization

2.6. Exploratory Efficacy Variables

Exploratory efficacy variables are as follows:

- Incidence of very severe RSV LRTI defined as RSV LRTI hospitalization with oxygen saturation < 90% (at any time during hospitalization) and oxygen supplementation, through Day 181 post-dosing/randomization (overall and in each country)
- Health care utilization
 - Duration of hospitalization
 - Admission to the intensive care unit and duration of stay
 - Number of participants who require oxygen supplementation
 - Number of participants who require intravenous fluid administration

2.7. Safety Variable(s)

Safety variables are as follows:

- Any immediate adverse events (AEs) reported in the 30 minutes after immunization
- Non-serious AEs from Day 1 (post-dosing/randomization) to Day 31
- Adverse events of special interest (AESIs) from Day 1 through 12-month post-dosing/randomization or Day 366
- Medically attended adverse events (MAAEs) from Day 1 through 12-month post-dosing/randomization or Day 366
- Serious adverse events (SAEs) from Day 1 through 12-month post-dosing/randomization or Day 366

- Related SAEs from Day 366 to Day 731 for UK re-consented participants

3. Estimand(s)

The ICH ⁴ E9 (R1) addendum on estimands⁵ and sensitivity analysis in clinical trials to the guideline on statistical principles for clinical trials came into effect on 30 July 2020. This section addresses the construction of estimands for the primary and key secondary objectives. Each estimand is defined according to the following five attributes:

- 1) The **treatment** condition of interest, and as appropriate, the alternative condition to which comparison will be made.
- 2) The **population** of participants targeted by the clinical question.
- 3) The **variable** (or endpoint) to be obtained for each participant that is required to address the clinical question.
- 4) The clinical question of interest in respect of **other intercurrent events** not covered through the precise specifications of treatment, population and variable.
- 5) A **population-level summary** for the variable providing a basis for comparison between treatment conditions.

3.1. Estimands for the primary objective(s)

The estimand for the primary efficacy objective is defined as as the overall incidence (measured by 1 minus the incidence rate ratio) of RSV LRTI hospitalization through the RSV season in healthy infants born ≥ 29 WGA entering their first RSV season and not eligible to palivizumab, who received nirsevimab on Day 1, compared to no intervention on Day 1, and detailed through the 5 attributes (including intercurrent events) described in Sections 3.1.1 to 3.1.7.

3.1.1. Treatment Condition of Interest

The primary treatment condition of interest is nirsevimab administration (dose of 50 mg for participants weighting < 5 kg at dosing/randomization and 100 mg for participants ≥ 5 kg at dosing/randomization) on Day 1 and is compared to no intervention on Day 1.

3.1.2. Population of Participants Targeted by the Clinical Question

The population targeted by the clinical question is defined through randomized healthy infants born ≥ 29 WGA entering their first RSV season and not eligible for palivizumab.

3.1.3. Variable Obtained from Each Participant Required to Address the Clinical Question

For each participant in the study, the variables to address the clinical question are the occurrence of RSV LRTI hospitalization through the RSV season (as defined in Section 2.4) and the follow-up time post-dosing/randomization up to the data cut-off date.

3.1.4. Handling of Intercurrent Events to Reflect the Clinical Question of Interest

The following intercurrent events are anticipated during the study:

- Participant ends study early and withdraws consent from further data collection
- Participant ends study early without withdrawing consent from further data collection
- Participant who received Beyfortus (nirsevimab) as a routine medication during the study

The following table describes how intercurrent events will be collected and handled within the analysis.

Table 2 Handling of Intercurrent Events for the Primary Estimand

Intercurrent event	Data collection and analysis
Participant ends study early and withdraws consent from further data collection	Participants who withdraw consent from further data collection will be analyzed by while on treatment strategy: only data collected before the occurrence of the intercurrent event will be included in the analysis. Participants will be censored at the earliest of: (i) last available date with no confirmation of RSV LRTI hospitalization, (ii) end of the RSV season or (iii) data cut-off date for the Primary Analysis (see section 6.7.8)
Participant ends study early without withdrawing consent from further data collection	Participants who end study early without withdrawing consent from further data collection will be analyzed with a treatment policy strategy: if RSV LRTI hospitalization occurs after cut-off date or end of the RSV season whichever is earlier, it will not be considered. Participants will be censored at the earliest of (i) last available date with no confirmation of RSV LRTI hospitalization, (ii) end of the RSV season or (iii) data cut-off date for the Primary Analysis
Participant who received Beyfortus (nirsevimab) as a routine medication during the study	Participants who received Beyfortus will be analyzed by while on treatment strategy: only data collected before the occurrence of the intercurrent event will be included in the analysis. Participants will be censored at the earliest of: (i) last available date with no confirmation of RSV LRTI hospitalization, (ii) end of the RSV season or (iii) data cut-off date for the Primary Analysis or (iv) start date of Beyfortus

3.1.5. Population-level Summary for Comparison between Treatment Conditions

The efficacy will be quantified by the incidence rate ratio (defined in section 6.6.1) and its corresponding 2-sided 95% Confidence Interval (CI), calculated using an exact method assuming a binomial distribution of the number of RSV LRTI hospitalizations in nirsevimab group conditional on total number of RSV LRTI hospitalizations in both groups.

The superior efficacy of nirsevimab in preventing RSV LRTI hospitalization will be concluded if the lower bound of 2-sided 95% CI of the treatment efficacy is $> 0\%$.

3.1.6. Sensitivity Estimators for the Primary Estimand

Sensitivity analyses within ICH E9 (R1) addendum evaluate the robustness of inferences from the main estimator to deviations from its underlying assumptions targeting the same estimand. The robustness of the main estimator will be explored using a Poisson Regression model as well as a tipping point analysis described in section 6.6.2.

3.1.7. Supplementary Analyses for the Primary Estimand

Supplementary analyses provide additional understanding of a treatment effect. Supplementary analyses with Per-Protocol Analysis Set and based on survival analysis are described in section 6.6.3.

3.2. Estimand for the 1st key secondary objective

The estimand for the 1st key secondary efficacy objective is defined as the overall incidence (measured by 1 minus the incidence rate ratio) of very severe RSV LRTI through the RSV season in healthy infants born ≥ 29 WGA entering their first RSV season and not eligible to palivizumab, who received nirsevimab on Day 1, compared to no intervention on Day 1, while participants are on treatment, and detailed through the 5 attributes (including intercurrent events) described in Sections 3.2.1 to 3.2.7.

3.2.1. Treatment Condition of Interest

The primary treatment condition of interest is nirsevimab administration (dose of 50 mg for participants weighting < 5 kg at dosing/randomization and 100 mg for participants ≥ 5 kg) on Day 1 and is compared to no intervention on Day 1.

3.2.2. Population of Participants Targeted by the Clinical Question

The population targeted by the clinical question is defined through randomized healthy infants born ≥ 29 WGA entering their first RSV season and not eligible for palivizumab.

3.2.3. Variable Obtained from Each Participant Required to Address the Clinical Question

For each participant in the study, the variable to address the clinical question is the occurrence of very severe RSV LRTI, defined as RSV LRTI hospitalization with oxygen saturation $< 90\%$ (at any time during hospitalization) and oxygen supplementation, through the RSV season.

3.2.4. Handling of Intercurrent Events to Reflect the Clinical Question of Interest

The following intercurrent events are anticipated during the study:

- Participant ends study early and withdraws consent from further data collection
- Participant ends study early without withdrawing consent from further data collection
- Participant who received Beyfortus (nirsevimab) as a routine medication during the study

The following table describes how intercurrent events will be collected and handled within the analysis.

Table 3 Handling of Intercurrent Events for the 1st key Secondary Estimand

Intercurrent event	Data collection and analysis
Participant ends study early and withdraws consent from further data collection	Participants who withdraw consent from further data collection will be analyzed by while on treatment strategy: only data collected before the occurrence of the intercurrent event will be included in the analysis. Participants will be censored at the earliest of: (i) last available date with no confirmation of RSV LRTI hospitalization, (ii) end of the RSV season or (iii) data cut-off date for the Primary Analysis
Participant ends study early without withdrawing consent from further data collection	Participants who end study early without withdrawing consent from further data collection will be analysed with a treatment policy strategy: if RSV LRTI hospitalization occurs after cut-off date or end of the RSV season, it will not be considered. Participants will be censored at the earliest of (i) last available date with no confirmation of RSV LRTI hospitalization, (ii) end of the RSV season or (iii) data cut-off date for the Primary Analysis.
Participant who received Beyfortus (nirsevimab) as a routine medication during the study	Participants who received Beyfortus will be analyzed by while on treatment strategy: only data collected before the occurrence of the intercurrent event will be included in the analysis. Participants will be censored at the earliest of: (i) last available date with no confirmation of RSV LRTI hospitalization, (ii) end of the RSV season or (iii) data cut-off date for the Primary Analysis or (iv) start date of Beyfortus

3.2.5. Population-level Summary for Comparison between Treatment Conditions

The efficacy in preventing very severe RSV LRTI will be quantified by the incidence rate ratio and its corresponding 2-sided 95% CI calculated using an exact method assuming a binomial distribution of the number of very severe RSV LRTI in nirsevimab group conditional on the total number of very severe RSV LRTI in both groups.

The superior efficacy of nirsevimab in preventing very severe RSV LRTI will be concluded if the lower bound of the 2-sided 95% CI of the efficacy is $> 0\%$ provided that the null hypothesis for the primary efficacy analysis has been rejected.

3.2.6. Sensitivity Estimators for the 1st key Secondary Estimand

The robustness of the main estimator will be explored using a Poisson Regression model as well as a tipping point analysis described in section [6.6.5.1](#).

3.2.7. Supplementary Analyses for the 1st key Secondary Estimand

Supplementary analyses with Per-Protocol Analysis Set and Time-to-event are described in section [6.6.6.1](#).

3.3. Estimands for the 2nd key secondary objective

The estimand for the 2nd key secondary efficacy objective is defined as the incidence (measured by 1 minus the incidence rate ratio) of RSV LRTI hospitalization through the RSV season in each country in healthy infants born ≥ 29 WGA entering their first RSV season and not eligible to palivizumab, who received nirsevimab on Day 1, compared to no intervention on Day 1, while participants are on treatment and detailed through the 5 attributes (including intercurrent events) described in Sections [3.3.1](#) to [3.3.7](#).

3.3.1. Treatment Condition of Interest

The primary treatment condition of interest is nirsevimab administration (dose of 50 mg for participants weighting < 5 kg at dosing/randomization and 100 mg for participants ≥ 5 kg) on Day 1 and is compared to no intervention on Day 1.

3.3.2. Population of Participants Targeted by the Clinical Question

The population targeted by the clinical question is defined through randomized healthy infants born ≥ 29 WGA entering their first RSV season and not eligible for palivizumab.

3.3.3. Variable Obtained from Each Participant Required to Address the Clinical Question

For each participant in the study, the variable to address the clinical question is the occurrence of RSV LRTI hospitalization through the RSV season in each of the 3 countries.

3.3.4. Handling of Intercurrent Events to Reflect the Clinical Question of Interest

The following intercurrent events are anticipated during the study:

- Participant ends study early and withdraws consent from further data collection
- Participant ends study early without withdrawing consent from further data collection
- Participant who received Beyfortus (nirsevimab) as a routine medication during the study

The following table describes how intercurrent events will be collected and handled within the analysis.

Table 4 Handling of Intercurrent Events for the 2nd key Secondary Estimand

Intercurrent event	Data collection and analysis
Participant ends study early and withdraws consent from further data collection	Participants who withdraw consent from further data collection will be analyzed by while on treatment strategy: only data collected before the occurrence of the intercurrent event will be included in the analysis. Participants will be censored at the earliest of: (i) last available date with no confirmation of RSV LRTI hospitalization, (ii) end of the RSV season or (iii) data cut-off date for the Primary Analysis
Participant ends study early without withdrawing consent from further data collection	Participants who end study early without withdrawing consent from further data collection will be analysed with a treatment policy strategy: if RSV LRTI hospitalization occurs after cut-off date or end of the RSV season, it will not be considered. Participants will be censored at the earliest of (i) last available date with no confirmation of RSV LRTI hospitalization, (ii) end of the RSV season or (iii) data cut-off date for the Primary Analysis
Participant who received Beyfortus (nirsevimab) as a routine medication during the study	Participants who received Beyfortus will be analyzed by while on treatment strategy: only data collected before the occurrence of the intercurrent event will be included in the analysis. Participants will be censored at the earliest of: (i) last available date with no confirmation of RSV LRTI hospitalization, (ii) end of the RSV season or (iii) data cut-off date for the Primary Analysis or (iv) start date of Beyfortus

3.3.5. Population-level Summary for Comparison between Treatment Conditions

The efficacy will be quantified with each country by the incidence rate ratio and its corresponding 2-sided 95% CI calculated using an exact method assuming a binomial distribution of the number of RSV LRTI hospitalizations.

If the null hypothesis for the 1st key secondary estimand is rejected (superiority of nirsevimab for preventing very severe RSV LRTI) then the efficacy within each country will be tested using a superiority approach. The Bonferroni adjusted 2-sided 95% CI will be presented and superiority assessed using the Bonferroni-Holm procedure. Adjustment will be performed for all sensitivity and supplementary analyses produced for this 2nd key secondary objective.

3.3.6. Sensitivity Estimators for the 2nd key Secondary Estimand

The robustness of the main estimator will be explored using a Poisson Regression model as well as a tipping point analysis described in section [6.6.5.2](#).

3.3.7. Supplementary Analyses for the 2nd key Secondary Estimand

Supplementary analyses with Per-Protocol Analysis Set and Time-to-event are described in section [6.6.6.2](#).

4. Analysis Populations

In accordance with ICH E3 and E9 ⁶, the following analysis sets will be used for the analyses.

4.1. All Screened Set

The All Screened Set will consist of all participants who have signed the informed consent forms. The All Screened Set will be used for summaries of disposition and the associated listing.

4.2. All Randomized Set

All Randomized Set will consist of all participants randomly assigned to either the nirsevimab group or the no intervention group. All Randomized Set participants are analyzed according to their randomized study intervention group.

4.3. Per-Protocol Analysis Set

The PPAS will consist of all randomized participants who do not have any important protocol deviations leading to exclusion from the PPAS. PPAS participants are analyzed according to their randomized study intervention group.

Protocol deviations are defined as any change, divergence, or departure from the study design or procedures defined in the study protocol. Important protocol deviations are a subset of protocol deviations which may significantly impact the correctness, accuracy, and / or reliability of the study data or that may significantly affect a participant's rights, safety, or well-being. Section 4.3.1 details the deviations.

4.3.1. Important Protocol Deviations Leading to Exclusion from the Per-Protocol Analysis Set

Deviations from the protocol, as defined in the protocol and / or protocol deviation plan, will be documented by the study monitors and project management throughout the study period.

Only those important protocol deviations considered to have a major effect on efficacy will lead to exclusion of the participant from the PPAS. For the purposes of this study, the following criteria have been identified as candidates for important protocol deviations leading to exclusion from the PPAS as it is considered that the occurrences of any of these criteria might have an important influence on the primary efficacy endpoint:

- Participant did not meet all protocol-specified inclusion criteria or met at least one of the protocol-specified exclusion criteria

- Participant did not receive nirsevimab or the correct dose of nirsevimab if randomized to nirsevimab
- Participant received nirsevimab if randomized to no intervention
- Administration of nirsevimab was not done as per-protocol
- Participant did not have at least one contact for efficacy follow-up after dosing/randomization (ie, eDiary was not completed by parents or phone call by Medical Call Center (MCC)/site to collect hospitalization information was not done).
- Participant who received Beyfortus (nirsevimab) as a routine medication during the study.
- Any other protocol deviations identified during the study conduct as relevant to the exclusion from the PPAS

Participants will be assessed purely by comparison of their eCRF data with the criteria above; protocol waivers or exemptions are not allowed.

Criteria which require clinical or medical monitoring interpretation will be reviewed prior to database lock. All important protocol deviations leading to exclusion from the PPAS occurring during the study will be reviewed and approved by the sponsor (ie, Sanofi Pasteur) prior to database lock. If additional important protocol deviations, which were not anticipated at the time of SAP preparation, are identified during the study and are deemed to lead to exclusion from the PPAS, such deviations will be documented in a SAP amendment and included in all relevant protocol deviation reviews and approvals.

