In order to minimize the burden on sites, families and participants, while still answering the objective of this protocol amendment, it was decided to invite in the study extension only the UK participants, who represent 50% of the study population.

Enrollment of Study Participants

A total of 28 860 participants will be enrolled from sites in France, Germany, and the United Kingdom. The study will enroll infants born either out of the RSV season or in the RSV season.

Definition of the RSV season

There is an important variability of RSV seasonality from year to year in each country. The typical RSV season in the Northern Hemisphere (NH) last approximately 5 months and usually starts in October or November. Therefore, the "Out-of-Season" period refers to the approximately 7 months period from March or April to September or October. The actual start date and length of the RSV season will depend on the actual circulation of RSV in the NH in 2022.

Cases of LRTI hospitalization will be collected throughout the study to ensure that all cases occurring during the next RSV season are captured. For the need of this study, the start and end dates of the RSV season will be defined on a country-by-country basis and will be based on country-specific epidemiological surveillance. For the mothers of infants to be born in-season, recruitment will start at 30 weeks gestation in women with an estimated delivery date during the RSV season.

Rationale for the Collection of Safety Data

Immediate AEs

As nirsevimab is not a marketed product, a 30 minutes immediate surveillance period of infants enrolled in the nirsevimab group will be done on the site where immunization was performed.

Non-serious AEs

For a period of 30 days post-dosing/randomization, non-serious AEs will be captured in the eCRF for all study participants. The relation of AEs to interventional product will be determined by the Investigator.

The use of the eDiary by parents and the process for reporting AEs in the eCRF is outlined in Section 8.2.3.

Hospitalizations

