 - for the participants who had no contact for safety events at all throughout the efficacy follow-up period, the end date for the efficacy follow-up will be date of randomization for participants who are randomized to no intervention, the date of treatment dosing for participants who are randomized to nirsevimab and treated, and the date of randomization for participants who are randomized to nirsevimab but not treated.

The total person-time for the follow-up time of each participant will be calculated as:

Person-months = (the end date - the start date + 1)/30.4375.

NN (days), the total person-time contributed by participants randomized in the nirsevimab, will be the sum of person-months for all the participants in the nirsevimab group. And NC (days), the total person-time contributed by participants randomized in the no intervention group, will be the sum of person-months for all the participants in the no intervention group.

The 2-sided 95% CI for the efficacy will be calculated by an exact method assuming a binomial distribution of the number of RSV LRTI hospitalizations in the nirsevimab group conditional on the total number in both groups (described by Breslow and Day⁷) accounting for the follow-up time post-dosing/randomization.

The superior efficacy of nirsevimab in preventing RSV LRTI hospitalization is concluded if the lower bound of 2-sided 95% CI of the efficacy is $> 0\%$. P-value will also be provided. The primary efficacy analysis of the primary endpoint will be performed with the All Randomized Set.

RSV season is the period of increased RSV infection. For the purpose of efficacy analyses, the start of the RSV season will be defined on a country-by-country basis and will be based on country-specific epidemiological surveillance and the cut-off date (28Feb2023, except for site parent contact and medical call center contact, for which the date of database lock for Primary Analysis will be used) will be used as end dates.

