6.7.8. Planned Analyses and Data Monitoring

There will be 3 planned main analyses for this study: the Primary Analysis, the First Year Analysis and the Second Year Analysis.

The Primary Analysis will be conducted when at least 61 events of RSV LRTI hospitalization in all 3 countries combined are observed, but no later than 30 April 2023. All available data collected up to the data cut-off date will be analyzed at the time of the Primary Analysis.

The First Year Analysis will be conducted when all participants have completed the scheduled 12-month safety follow up. It will include all data and planned analyses. The Second Year Analysis will be conducted when all UK reconsented participants have completed the scheduled 24-month safety follow-up. It will include all data and planned analyses. In order to present results from the First Year Analysis or Second Year Analysis, results may be generated before the formal lock of data for abstract purposes. Updates of the data will be done with the formal database locks.

A Primary Analysis is planned prior to the formal completion of the study. The efficacy analyses planned in the Primary Analysis will serve the purpose of evaluating the efficacy of nirsevimab in the study population.

In addition, Primary Analysis outputs will also be rerun at the time of First Year Analysis still with the same cut-off date in order to consider potential new data collected after the cut off date due to the delay in the data collection (see Section 6.6.7.10 for details).

RSV LRTI hospitalization will also be collected after the end of the RSV season and the efficacy will be calculated but only for descriptive purposes at the time of the First Year Analysis without the intention of a confirmatory conclusion.

This will also be collected at 24 months follow-up in UK reconsented participants but only for descriptive purposes at the time of the Second Year Analysis without the intention of a confirmatory conclusion.

In addition, recurrent wheeze event will be collected at the 12 and 24 months follow-up, in UK reconsented participants only for descriptive purposes at the time of the Second Year Analysis.

Therefore, no multiplicity adjustment is needed for the 3 main analyses (Primary, First Year and Second Year) of the primary endpoint.

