- ✓ For LRTI description, the rule “*If participants have multiple hospitalizations (respectively ICU stay) during the follow up period, duration of hospitalization (respectively ICU stay) will be the sum of each duration of hospitalization (respectively ICU stay)*” was finally not applied for Primary Analysis and will not be considered for First Year Analysis.

The following changes were performed for First Year Analysis:

- ✓ Incidence of hospitalizations for all-cause LRTI through Day 181 post-dosing/randomization will also be analysed by country
- ✓ Incidence of very severe RSV LRTI defined as RSV LRTI hospitalization with oxygen saturation < 90% (at any time during hospitalization) and oxygen supplementation, through Day 181 post-dosing/randomization will also be described by country

Tables for transparency will also be produced at the time of Second Year Analysis.

The Primary Analysis was re-run at the time of the First Year Analysis considering the same cut-off date and the same rules as the Primary Analysis.

An additional intercurrent event was added to consider participants who received Beyfortus as a routine medication during the study. They are excluded from the Per-Protocol Analysis Set and some analyses and listings are produced restricted to these specific participants (if at least 10 participants for tables / if at least one participant for listings).

8. Appendices

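### The per-protocol exclusion for routine Beyfortus has no time limit, so the First Year per-protocol re-run can drop infants for a dose given after their endpoint follow-up had ended

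*SAP*

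**What the plan says.** SAP 4.3.1 lists "Participant who received Beyfortus (nirsevimab) as a routine medication during the study" among the deviations leading to exclusion from the PPAS. It sets no limit by date, arm or event status. The section justifies its criteria on the ground that they "might have an important influence on the primary efficacy endpoint". SAP Section 7 repeats the rule without qualification: "They are excluded from the Per-Protocol Analysis Set and some analyses and listings are produced restricted to these specific participants".

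The main estimand treats the same event differently. In SAP 3.1.4, Table 2, "only data collected before the occurrence of the intercurrent event will be included in the analysis", and the infant is censored at the earliest of several dates, the last listed being "or (iv) start date of Beyfortus".

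SAP 6.6.1 ends the RSV season for analysis at "the cut-off date (28Feb2023, except for site parent contact and medical call center contact". I read the exception as covering when contacts may confirm an infant's status, not as extending the season. The PPAS efficacy analyses (SAP 6.6.3.1, 6.6.6.1.1 and 6.6.6.2.1) all concern through-season endpoints.

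On timing, SAP 6.7.8 says that "Primary Analysis outputs will also be rerun at the time of First Year Analysis still with the same cut-off date", and SAP 6.6.7.10 says the re-run follows the rules of the Primary Analysis. The SAP document history dates the Beyfortus exclusion to version 4.0 of 22 December 2023. The Primary Analysis was due by 30 April 2023. The PPAS definition in Protocol 9.3 has no Beyfortus criterion.

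**The concern.** A per-protocol set should be defined by what happened up to the end of the outcome window. A dose given later cannot change whether the infant was hospitalized within the window, so it does not meet the rationale that SAP 4.3.1 gives for its own criteria. It can still be related to the outcome. The study is open-label, so families know whether their infant was protected, and a hospital stay for RSV may change whether a routine dose is sought later. Excluding on such an event selects on the future, and the rate ratio shifts if the selection differs by arm and event status.

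The PPAS result is a planned check on the primary result. If it moves, a reader cannot tell whether the cause is adherence or the selection rule. The new criterion may also mean that the Primary Analysis PPAS and the re-run PPAS are different populations, although they share a cut-off date.

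**Working it through.** **1. How much study time lies after the window.** Planned enrolment runs from 1 September 2022 to 28 February 2023 (Protocol 4.1), and the window ends on 28 February 2023.
- Enrolled 1 September 2022: 181 days inside the window, so 366 − 181 = 185 of 366 days (51%) fall after it.
- Enrolled 28 February 2023: 1 day inside, so 365 of 366 days (99.7%) fall after it.

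At least half of each infant's first year is time in which a dose triggers exclusion but cannot affect the endpoint.

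**2. The two rules side by side.** Take an infant given Beyfortus after 28 February 2023. Under Table 2 the season end comes first, so the infant keeps all of its in-window follow-up in the All Randomized Set. Under SAP 4.3.1 the same infant contributes nothing to the PPAS.

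**3. The plan's own figure.** Protocol 9.2 assumes 1.1% control incidence, 60% efficacy and 9620 infants per country (4810 per arm). Expected events are 4810 × 0.011 × (1 + 0.4) = 74.1, which matches the stated 74.

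**4. Planning case for all countries combined.** With 14 430 per arm, control events are 14 430 × 0.011 = 159, and nirsevimab events are 14 430 × 0.011 × 0.4 = 63. Assuming equal in-window follow-up per infant, efficacy = 1 − (63/14 430)/(159/14 430) = 60.4%. The exact conditional 95% CI is 46.6 to 70.9.

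**5. Effect of exclusion.** The documents give no uptake, so every removal fraction here is an assumption. Removing 10% of event-free controls leaves a control denominator of 159 + 0.9 × 14 271 = 13 002.9. Efficacy is then 1 − (63/14 430)/(159/13 002.9) = 64.3%. The other rows use the same method.

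| Assumed removal from the PPAS | Efficacy, % (95% CI) |
|---|---|
| None | 60.4 (46.6 to 70.9) |
| 1% of event-free controls | 60.8 (47.2 to 71.2) |
| 5% of event-free controls | 62.3 (49.3 to 72.3) |
| 10% of event-free controls | 64.3 (51.9 to 73.8) |
| 20% of event-free controls | 68.2 (57.2 to 76.6) |
| 10% of event-free controls, 5% of control cases | 62.4 (49.3 to 72.5) |
| 10% of event-free controls, 5% of event-free nirsevimab infants | 62.4 (49.4 to 72.4) |
| 10% of all controls, whatever their event status | 60.4 (46.4 to 71.0) |
| 10% of event-free infants in both arms | 60.3 (46.6 to 70.9) |
| 10% of event-free nirsevimab infants only | 56.0 (40.7 to 67.7) |
| 10% of event-free controls, 20% of control cases | 55.5 (39.3 to 67.6) |

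At the lowest control incidence in Protocol 9.2 (0.86%), the base is 59.7%. Removing 10% of event-free controls only gives 63.7%, and 10% of event-free nirsevimab infants only gives 55.2%.

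**6. Very low uptake.** Removing 10 event-free controls gives 1 − (63/159) × (14 420/14 430) = 60.40%, against 60.38% before. Removing 100 gives 1 − (63/159) × (14 330/14 430) = 60.65%.

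**The case against.** **The direction is not known.** A reader might infer that the rule removes event-free controls and so inflates efficacy. The documents do not support that. The criterion covers both arms, and cases as well as non-cases. An upward shift needs higher uptake in event-free controls than in control cases, not matched among event-free nirsevimab infants. That is plausible in an open-label trial, but it is an assumption. This objection stands.

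**Uptake may be very small.** The SAP produces several Beyfortus tables only if at least 10 infants are concerned, so its authors allowed for fewer. Step 6 shows that the effect would then be negligible. The objection stands as to size. The equal-follow-up assumption matters too: infants enrolled last stay in the study longest after the window but contribute little time within it, so removing them would matter less.

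**The timing of doses is not documented.** Protocol 4.2 says "As nirsevimab is not a marketed product", and Protocol 6.8 foresees commercial availability during the study. Neither gives a launch date, so the number of doses given after the window cannot be worked out. This also stands.

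**The result is supplementary.** The primary test uses the All Randomized Set, and the criterion came in after the Primary Analysis was due. No second-year PPAS efficacy run is specified. No confirmatory conclusion can change.

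**Sponsor review could keep such infants in.** SAP 4.3.1 calls its criteria candidates, reserves exclusion for deviations with a major effect on efficacy, and requires sponsor approval before database lock. But it also says that participants are assessed purely by comparing eCRF data with the criteria, and Section 7 states the exclusion as a fact. Review does not settle the point.

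**A per-protocol set may exclude where the estimand censors.** That is a fair choice for a dose inside the window. It gives no reason to exclude for a dose after it.

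**Conclusion.** The point holds as a defect in a supplementary analysis. As written, the PPAS can exclude infants for an event after their outcome was complete, contrary to the rationale for the criteria and unlike the handling in Table 2. Whether this reaches the First Year re-run depends on which text governs: the current SAP 4.3.1, or the commitment in SAP 6.6.7.10 to the rules of the Primary Analysis. The SAP does not say.

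The size cannot be fixed from the documents. Under the planning rates and equal follow-up, the shift runs from nothing, with balanced removal or a handful of exclusions, to about 4 percentage points up (64.3%) or 4 to 5 down (56.0% or 55.5%) in the scenarios built on 10% removal. Larger one-sided uptake would move it further. A claim that PPAS efficacy is inflated would go beyond the evidence. What is shown is that the rule permits bias in either direction and that one phrase removes it.

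**What to change.** 1. In SAP 4.3.1, limit the criterion to routine Beyfortus received on or before the end of the infant's efficacy follow-up for the endpoint analysed. Alternatively, drop the criterion and censor as in Table 2.
2. Apply the same time limit to the separate criterion that removes controls who received nirsevimab. Beyfortus is nirsevimab, so that criterion read literally would still exclude a control dosed after the window, even with the first one amended or deleted. It also stands in Protocol 9.3, so record the clarification in SAP Section 7.
3. State in SAP 6.6.7.10 whether the Beyfortus criterion applies to the First Year re-run.
4. Report the infants excluded under these two criteria by arm, event status, and dose before or after the end of follow-up, so that readers can judge any shift.

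The cost is two phrases, one sentence and one small table, with no new data beyond the Beyfortus dates that Table 2 censoring already needs. SAP Section 7 describes the re-run in the past tense. If it has already been produced, the practical step is to repeat the PPAS tables with the limit applied and say which criterion the existing ones used.
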